4.2 Exclusion Criteria

Subjects who meet any of the following criteria will be excluded from the study:

- 4.2.1 Pregnancy or breast-feeding.
- 4.2.2 Known allergy/sensitivity or any hypersensitivity to components of study drug(s) or their formulation.
- 4.2.3 Known cardiovascular disease (history of MI, coronary artery bypass graft surgery, percutaneous coronary intervention, stroke, transient ischemic attack, peripheral arterial disease with ABI <0.9 or claudication).
- 4.2.4 Uncontrolled type II diabetes mellitus.
- 4.2.5 Known chronic inflammatory conditions such as, but not limited to, rheumatoid arthritis, systemic lupus erythematosus, sarcoidosis, inflammatory bowel disease (i.e., Crohn's disease or ulcerative colitis), chronic pancreatitis, or autoimmune hepatitis, myositis, or myopathy.
- 4.2.6 History of asthma requiring medical treatment within 2 years prior to study entry with the exception of the use of albuterol inhaler for mild intermittent asthma.
- 4.2.7 Serious illness requiring systemic treatment and/or hospitalization within 14 days prior to entry.
- 4.2.8 Use of any of the following medications for more than 3 consecutive days within the 60 days prior to study entry:
 - Immunosuppressives (e.g., azathioprine, , cyclosporine, mycophenolate, sirolimus, sulfasalazine, tacrolimus)
 - Immune modulators (e.g., cytokines [e.g., IL-2], granulocyte colony stimulating factor, growth hormone, tumor necrosis factor antagonists, thalidomide)
 - Antineoplastic agents
 - Anticoagulants (e.g., warfarin and heparin)
 - Anti-platelet drugs (e.g., clopidogrel)
- 4.2.9 Use of any of the following medications for more than 3 consecutive days within the 30 days prior to study entry:
 - Corticosteroids [physiologic replacement doses are allowed]
 - NSAIDs (nonsteroidal anti-inflammatory drugs)
 - Aspirin
- 4.2.10 Vaccinations within 1 week prior to the pre-entry or study entry visits.

NOTE: Routine standard of care vaccinations including hepatitis A and/or B, influenza, pneumococcal, and tetanus are permitted if administered at least 7 days before pre-entry and entry evaluations.

4.2.11 Participation on any HIV immunotherapy or therapeutic vaccination trials within 6 months prior to study entry.

4.2.12 Active drug or alcohol use or dependence that, in the opinion of the site investigator, would interfere with adherence to study requirements.

4.2.13 Use of investigational therapies within 30 days prior to study entry.

4.2.14 Rectal Tissue Subset only:

- Abnormalities of the colorectal mucosa or significant colorectal symptom(s), which in the opinion of the study investigator represent a contraindication to biopsy (including but not limited to presence of any unresolved injury, infectious or inflammatory condition of the local mucosa, and presence of symptomatic external hemorrhoids.

NOTE: Abnormalities of the colorectal mucosa will be assessed at the time of the enrollment flexible sigmoidoscopy. If no significant colorectal abnormalities or symptoms are present then the participant will undergo the enrollment procedures. If abnormalities are present then no biopsies will be performed and the participant will not be enrolled into the rectal tissue subset but will continue participation in the main study.

- Active untreated gonorrhea, or chlamydia infection within 30 days prior to study entry (subjects diagnosed with rectal gonorrhea or chlamydia infection at screening may be treated during the screening period provided the treatment is at least 30 days prior to entry).

4.2.15 Exclusions for spirometry testing (for participants enrolled under Version 2.0): Participants will not undergo pre- and post-bronchodilator spirometry if they have any of the following:

- Abdominal or cataract surgery within 3 months.
- Myocardial infarction or stroke within the past 3 months.
- Acute onset of shortness of breath, cough, fever or heart condition such as tachycardia, angina or arrhythmias with 4 weeks prior to enrollment.
- Increasing respiratory symptoms or febrile (temperature >100.4°F [38°C]) within 4 weeks of study entry.
- Uncontrolled hypertension defined as systolic > 160 mm Hg or diastolic > 100 mm Hg from an average of two or more readings. Participant with controlled hypertension may undergo spirometry.
- Prior history of adverse reaction to albuterol

4.3 Study Enrollment Procedures

Prior to implementation of this protocol, and any subsequent full version amendments, the protocol and the protocol consent form(s) will be approved by the University of

Pittsburgh Institutional Review Board (IRB). Upon receiving final approval, all required protocol registration documents will be submitted to the DAIDS Protocol Registration Office (DAIDS PRO) at the Regulatory Support Center (RSC). The DAIDS PRO will review the submitted protocol registration packet to ensure that all of the required documents have been received.

4.4 Coenrollment Guidelines

Coenrollment into observational studies is permitted provided maximum blood draw volumes are not exceeded.

5.0 STUDY TREATMENT

5.1 Regimens, Administration, and Duration

Study treatment is defined as DP 100 mg capsules and matching placebo, and will be provided by the study. Subjects will be asked to bring back their study product bottles for pill counts for all post-entry visits.

5.1.1 Regimens

At study entry, subjects will be randomized to one of the following arms:

Arm A: Dipyridamole 100 mg 4 times daily for 24 weeks

Arm B: Dipyridamole placebo 1 capsule 4 times daily for 12 weeks, then Dipyridamole 100 mg 4 times daily for 12 weeks.

5.1.2 Administration

DP capsules (and Placebo capsules) should be taken orally 4 times daily with or without food.

5.1.3 Study Treatment Duration

Subjects will remain on study treatment until Week 24.

5.2 Study Product Formulation and Storage

DP 100 mg and placebo for DP are provided as capsules.

Store at a controlled room temperature of 25°C (77°F); excursions permitted to 15°-30°C (59°-86°F); protect from excessive moisture.

5.3 Pharmacy: Product Supply, Acquisition, and Accountability

5.3.1 Study Product Supply

DP and placebo for DP will be supplied by the Investigational Drug Service (IDS) of the University of Pittsburgh Medical Center.

5.3.2 Study Product Accountability

The IDS pharmacist will maintain complete records of all study products received and subsequently dispensed. All unused study products must be returned to IDS and will be destroyed after the study is completed or terminated.

5.4 Concomitant Medications

5.4.1 Required Medications

Subjects must be on combination ART (not provided by the study) as specified in the inclusion criteria (4.1.3).

5.5 Adherence Assessment

Pill counts and self-report adherence interviews for DP will be used to assess adherence during the treatment period. Subjects will be asked to bring in the bottles of study medication so that pill counts may be performed.

6.0 CLINICAL AND LABORATORY EVALUATIONS

6.1 Schedule of Events (SOE)

| Evaluation | Screening | Pre-Entry ¹ | Entry | Week | | | | | | | | Premature Treatment and/or Study Discontinuation | | |
|--|-----------|------------------------|-------|------|---|---|----|----|----|----|----|--|----|----------------|
| | | | | 2 | 4 | 8 | 12 | 14 | 16 | 20 | 24 | | 28 | |
| Documentation of HIV-1 infection | X | | | | | | | | | | | | | |
| Medical History/Medication History | X | | | | | | | | | | | | | |
| Complete Physical Exam | X | | | | | | | | | | | | | |
| Targeted Physical Exam | | X | X | | X | X | X | | X | X | X | X | | X |
| Clinical Assessments | | | X | | X | X | X | | X | X | X | X | | X |
| Concomitant Medications | | X | X | | X | X | X | | X | X | X | X | | X |
| Hematology | X | | X | | | | X | | | | X | | | X |
| Liver Function Tests/Blood Chemistries | X | | X | | X | | X | | X | | X | | | X |
| Fasting Lipid Panel | | | X | | | | X | | | | X | | | X |
| Plasma HIV-1-1 RNA | X | | X | | | | X | | | | X | | | X |
| CD4+/CD8+ | X | | X | | | | X | | | | X | | | X |
| Pregnancy Test | X | | X | | X | X | X | | X | X | X | X | | X |
| Prothrombin time/INR/PTT ² | | X | | | | | | | | | | | | |
| Hepatitis B and C | X | | | | | | | | | | | | | |
| Stored Plasma for Immunology/Virology ⁵ | | X | X | | X | | X | | X | | X | X | | X |
| Stored PBMC for Immunology/Virology ⁵ | | X | X | | X | | X | | X | | X | X | | X |
| Urine adenosine level (stored) ⁵ | | | X | | X | | X | | X | | X | | | X |
| Serum for Dipyridamole concentration (stored) | | | | | X | X | X | | X | X | X | | | X |
| Brachial Artery FMD | | | X | | X | | X | | | | X | | | X ³ |
| Rectal swabs for GC/CT NAAT ² | X | | X | | | | X | | | | X | X | | |
| HSV Serology ² | | | X | | | | | | | | | | | |
| Flexible sigmoidoscopy (rectal biopsy) ^{2, 5} | | | X | | | | X | | | | X | X | | |
| Adherence self-report | | | | | X | | X | | X | | X | | | |

| Evaluation | Screening | Pre-Entry ¹ | Entry | Week | | | | | | | | Premature Treatment and/or Study Discontinuation | |
|--|-----------|------------------------|-------|------|---|---|----|----|----|----|----|--|----|
| | | | | 2 | 4 | 8 | 12 | 14 | 16 | 20 | 24 | | 28 |
| Medication Adherence Assessment ⁴ | | | X | | X | | X | | X | | X | | |
| Telephone assessment of tolerability/adherence | | | | X | | | | X | | | | | |
| Pre- and post-bronchodilator spirometry ⁶ | | | X | | X | | X | | | | X | | |

- 1 Pre-Entry evaluations must be completed within 14 days prior to study entry.
- 2 Rectal Tissue sub-group only.
- 3 Only if ≥ 4 weeks since the last FMD assessment and on study medication ≤ 72 hours prior to visit.
- 4 Capsule counts to take place at all post-entry visits.
- 5 See Section 6.3.9 for specific assays.
- 6 For participants enrolled under Version 2.0

6.2 Timing of Evaluations

6.2.1 Screening and Pre-Entry Evaluations

Screening and pre-entry evaluations must occur prior to the subject's starting any study medications, treatments, or interventions.

Screening

Screening evaluations to determine eligibility must be completed within 60 days prior to study entry unless otherwise specified.

Pre-Entry

Pre-entry evaluations must be completed at least 24 hours after screening evaluations have been completed and within 14 days prior to study entry.

6.2.2 Entry Evaluations

Entry evaluations must occur at least 24 hours after pre-entry evaluations unless otherwise specified. All entry evaluations must be completed before study drug is started. In order to facilitate scheduling of procedures, subjects may have the FMD test or the rectal biopsies performed on a separate day within 3 days after randomization (but prior to starting study medication).

6.2.3 Post-Entry Evaluations

On-Study Evaluations

All on-study evaluations must be scheduled as per Section 6.1 with a ± 7 day window for all visits. In order to facilitate scheduling of procedures, subjects may have the FMD test or the rectal biopsies performed on a separate day within the visit window.

6.2.4 Discontinuation Evaluations

Evaluations for Randomized Subjects Who Do Not Start Study Treatment

Subjects who are randomized but do not start study treatment within 72 hours will be taken off study with no further evaluations required. All case report forms (CRFs) must be completed for the period up to and including week 0.

Premature Treatment Discontinuation Evaluations

Subjects who prematurely discontinue study treatment will have a study discontinuation visit as per Section 6.1 and then be taken off study.

6.2.5 Pregnancy

If a woman becomes pregnant while on study, study product will be discontinued immediately and no further study assessments will be performed except safety labs. See Section 7.2 regarding patient management. All pregnancies should be followed by monthly telephone contact until the final outcome can be determined.

In the event that the pregnancy has not been completed by the final study visit, then the subject will be contacted through monthly phone calls and review of medical records, if possible, until the pregnancy outcome can be ascertained. Intrapartum complications and/or pregnancy outcome will be recorded on the CRFs.

6.3 Instructions for Evaluations

All clinical and laboratory information required by this protocol is to be present in the source documents. Sites must refer to the Source Document Guidelines on the DAIDS Web site for information about what must be included in the source document: <http://www3.niaid.nih.gov/research/resources/DAIDSClinRsrch/PDF/SourceDocAppndx.pdf>. All stated evaluations are to be recorded on the CRF and keyed into the database unless otherwise specified. This includes events that meet the International Conference on Harmonization (ICH) definitions for a serious adverse event.

- Results in death
- Life-threatening
- Requires inpatient hospitalization or prolongation of existing hospitalization
- Results in persistent or significant disability/incapacity
- Congenital anomaly/birth defect
- Other important medical event (may not be immediately life-threatening or result in death or hospitalization but may jeopardize the subject or may require intervention to prevent one of the events listed above.

To grade diagnoses, signs and symptoms, and laboratory results, sites must refer to the DAIDS Table for Grading the Severity of Adult and Pediatric Adverse Events (DAIDS AE Grading Table), Version 1.0, December 2004 (Clarification, August 2009), which can be found on the DAIDS RSC Web site: <http://rsc.tech-res.com/safetyandpharmacovigilance>

6.3.1 Definition of Fasting

Subjects must be evaluated in a fasting state for those evaluations indicated as “fasting”.

NOTE: Fasting is defined as nothing to eat or drink except water and required prescription medications for at least 8 hours. Drinking black decaffeinated coffee without sweetener or creamer is permissible, but is not advised. Subjects will be asked whether they have fasted, and if not, they should be scheduled to return in a fasting state within 7 days.

Although subjects must be fasting, they will be specifically instructed to take all medications according to their regular schedules and with the usual amounts of water, to the extent that they can tolerate them in a fasting condition. Drugs that need to be taken with food may be brought to the clinic and taken with food after the FMD evaluation and the fasting specimen collection.

In order to minimize diurnal variation, fasting samples for individual subjects should be obtained consistently in either the morning or the afternoon throughout

the study, if possible.

6.3.2 Documentation of HIV-1

Please refer to Section 4.1.1 regarding assay requirements for HIV-1 documentation. HIV-1 documentation is not recorded on the CRF.

6.3.3 Medical History

The medical history must include all HIV-related and AIDS-defining diagnoses (Centers for Disease Control and Prevention [CDC] category B and C), and the following non-HIV diagnoses: diabetes mellitus, dyslipidemia, hypertension, hypotension, MI, coronary artery disease (not MI), congestive heart failure, stroke, malignancy, renal insufficiency, liver disease, pulmonary embolism, deep vein thrombosis, peripheral artery disease (including peripheral artery revascularization), chronic obstructive pulmonary disease (COPD), and asthma. Any allergies to any medications and their formulations must be documented in the source documentation.

HIV-1 RNA History

Pre-ART HIV-1 RNA: Record on the CRF the documented date and level of the subject's pre-ART viral load. If documentation is not available, then subject recollection will suffice.

Record on the CRF the documented date and viral load of the subject's first HIV-1 RNA level that was below the assay lower limit. Also, record the duration of time prior to study entry the subject has had continued HIV-1 RNA levels that were below assay lower limits. If documentation is unavailable, then subject recollection will suffice.

All known HIV-1 RNA levels obtained within 1 year prior to study entry should be documented and recorded on the CRF.

CD4+ T-cell History

Nadir CD4+ T-cell Count: The subject's nadir CD4+ T-cell count (absolute value and date) should be documented when possible with a copy of the nadir CD4+ T-cell count report. If this documentation is not available, then subject recollection will suffice. For subjects who do not know the exact nadir value and for whom there is no source documentation, then recall of the categorical nadir (e.g., < 50, < 100, < 200 cells/mm³) will suffice.

All known CD4+ T-cell counts obtained within 1 year prior to study entry should be documented and recorded on the CRF.

6.3.4 Medication History

A medication history must be present, including start and stop dates, in the source documents and on the CRFs, including:

Complete HIV-1 treatment history of any ARV medication (estimated if the exact dates cannot be obtained), immune-based therapy, and HIV-related vaccines, including blinded study medications.

All prescription medications and non-prescription drugs, including herbal supplements or vitamin supplements taken within 30 days prior to study entry.

6.3.5 Clinical Assessments

Complete Physical Examination

A complete physical examination is performed at Screening and is to include at a minimum an examination of the skin, head, mouth, and neck; auscultation of the chest; cardiac exam; abdominal exam; examination of the extremities for edema. The complete physical exam will also include signs and symptoms, diagnoses, height, weight, and vital signs (temperature, pulse, respiration rate, and blood pressure).

Targeted Physical Exam

A targeted physical examination is performed at Entry and all other study visits to include weight and vital signs (temperature, pulse, respiration rate, and blood pressure) and is to be driven by any previously identified or new signs or symptoms, or any diagnoses that the subject has experienced within 30 days prior to entry/since the last visit.

Height

Height will be recorded on the CRF at the screening visit only.

Weight

Weight will be recorded on the CRF at each targeted physical exam.

Signs and Symptoms

At entry, all grades that occurred within 30 days before study entry must be recorded; post-entry, only new signs and symptoms Grade ≥ 2 must be recorded on CRFs. Record on CRFs all signs and symptoms that led to a change in treatment, regardless of grade. The source document must include date of onset and date of resolution.

Diagnoses

After entry, record all HIV-related and AIDS-defining diagnoses (Centers for Disease Control and Prevention [CDC] category B and C), and the following non-HIV diagnoses: diabetes mellitus, dyslipidemia, hypertension, hypotension, MI, coronary artery disease (not MI), congestive heart failure, stroke, malignancy, renal insufficiency, liver disease, pulmonary embolism, deep vein thrombosis, peripheral artery disease (including peripheral artery revascularization), chronic obstructive pulmonary disease (COPD), and asthma.

Each diagnosis must include:

- a) Date of diagnosis, and date of resolution
- b) Method of diagnosis

Concomitant Medications

Record new, or discontinued concomitant medications including immune-based therapy, blinded study treatment, prescription drugs, nonprescription drugs, alternative therapies, and dietary supplements since the last visit.

Study Drug Modifications

Record all study drug modifications, including initial doses, subject-initiated and/or protocol-mandated modifications, and inadvertent and deliberate interruptions. Record any permanent discontinuation of treatment on the CRF. More than three consecutive missed days will be considered an interruption and should be recorded on the CRF.

Antiretroviral Therapy

All modifications to ART medications including initial doses, subject-initiated modifications (more than three consecutive missed days), modifications, and permanent discontinuation will be recorded on the CRFs.

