 - Total bilirubin $\leq 2.5 \times$ ULN (except if hyperbilirubinemia is secondary to atazanavir).
 - Creatinine $\leq 1.5 \times$ ULN
 - Hepatitis B surface antigen negative
 - Hepatitis C antibody negative (note: subject with HCV Ab positive is eligible if Hepatitis C RNA PCR (viral load) is undetectable)
- 4.1.9 For women of reproductive potential, negative serum or urine pregnancy test, with a sensitivity of ≤ 50 mIU/mL, at screening and within 72 hours prior to study entry.
- 4.1.10 Female study volunteers of reproductive potential include women who have not been post-menopausal for at least 24 consecutive months, (i.e., who have had menses within the preceding 24 months, or women who have not undergone surgical sterilization, specifically hysterectomy and/or bilateral oophorectomy).

If participating in sexual activity that could lead to pregnancy, female subjects must agree to use one form of contraceptive as listed below while receiving protocol-specified treatment and for 4 weeks after stopping the treatment.

- Condoms (male or female) with or without a spermicidal agent. Condoms are recommended because their appropriate use is the only contraception method effective for preventing HIV transmission.
- Diaphragm or cervical cap with spermicide
- Intrauterine device (IUD)
- Hormone-based contraceptive

NOTE: If the subject is taking a concomitant medication with stricter contraceptive requirements than what are listed in the protocol for the study drugs (such as in the case of efavirenz), then refer to the pregnancy category and product labeling for the concomitant medication with the strictest contraceptive requirements.

- 4.1.11 If the female subject is not of reproductive potential (girls who have not reached menarche, women who have been post-menopausal for at least 24 consecutive months, or women who have undergone surgical sterilization, e.g., hysterectomy, bilateral oophorectomy, or bilateral tubal ligation or salpingectomy), she is eligible without requiring the use of a contraceptive. Self-report is acceptable documentation of sterilization, other contraceptive methods, and menopause.
- 4.1.12 Rectal Tissue Subset only: Willing to abstain from receptive anal intercourse and practices involving insertion of anything in the rectum (drug, enema, penis, or sex

toy) for 72 hours prior to rectal biopsy and for 7 days post-biopsy to minimize risk of bleeding complications.

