6.3.6 Laboratory Evaluations

At screening and entry all protocol required laboratory values must be recorded on CRFs. For post-entry assessments, record on CRFs all Grade ≥ 2 laboratory values. All laboratory toxicities that led to a change in treatment, regardless of grade, must be recorded on CRFs. Record on CRFs all values for serum creatinine, AST, ALT, and fasting lipid panel regardless of grade.

Hematology

Hemoglobin, hematocrit, white blood cell count (WBC), differential WBC, and platelet count.

Liver Function Tests/Chemistries

Total bilirubin (and indirect bilirubin if subject is receiving atazanavir), ALT (SGPT), AST (SGOT), and alkaline phosphatase, blood urea nitrogen (BUN), creatinine, glucose, sodium, potassium, chloride, and CO₂/bicarbonate.

Fasting Lipid Panel

Total cholesterol, HDL-c, calculated LDL-c (if triglycerides <400 mg/dL) and triglycerides.

Hepatitis Testing (at Screening)

Hepatitis B surface antigen, Hepatitis C antibody (if indicated, Hepatitis C RNA PCR).

Prothrombin time/INR/PTT

Prothrombin time/INR and PTT are required at pre-entry for rectal tissue subset only.

Rectal GC/CT NAAT

Rectal swab for GC/CT NAAT will be obtained for rectal tissue subset only

HSV Antibody

Serum for HSV antibody testing will be obtained at Entry visit for the rectal tissue subset only

Pregnancy Test

For women of reproductive potential as defined in section 4.1.11, serum or urine β -HCG (urine test must have a sensitivity of at least 50 mIU/mL) must be performed as indicated in section 6.1:

- At the screening visit.
- At the study entry visit.
- Every 4 weeks during study participation.

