7.1.4 Headache

- Grade 1

Subjects who develop Grade 1 headache may continue study medications.

- Grade 2

Subjects who develop Grade 2 headache may continue study medication and may be treated with over the counter analgesics (acetaminophen preferred, NSAIDS should be avoided and may not be taken for > 3 consecutive days).

- Grade 3

Subjects who develop Grade 3 or 4 headache that is judged by the investigator to be related to DP will have study treatment permanently discontinued.

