9.2.2 Secondary Endpoints

- Changes from entry to week 12 and 24 (as applicable) in the following:
 - %HLA-DR+ CD38+ expression in CD8+ and CD4+ T-cells
 - %CD69+CD25+ expression in CD4+ and CD8+ T-cells
 - CD16 and tissue factor expression in monocytes
 - Plasma levels of biomarkers of systemic inflammation (sTNF α R, TNF α , hsCRP) and coagulation (D-dimer, tissue factor)
 - Percent brachial artery FMD
 - Proportion of cycling CD4+ and CD8+ T cells as measured by Ki-67 expression
- Grade 2 or higher AEs, treatment discontinuations
- Correlation of plasma DP level to urine adenosine, plasma IL-6, and soluble and cellular markers of immune activation

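### Section 6.3.5 requires only new Grade ≥2 symptoms on the CRF after Entry, so a symptom present at Entry that worsens to Grade 2 without a treatment change can go unrecorded

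*Combined protocol and SAP*

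**What the plan says.** Section 6.3.5 (Clinical Assessments) has one rule for symptoms at Entry and a narrower one afterwards. The Entry rule is inclusive: "At entry, all grades that occurred within 30 days before study entry must be recorded". After that, "post-entry, only new signs and symptoms Grade ≥ 2 must be recorded on CRFs". One exception follows: "Record on CRFs all signs and symptoms that led to a change in treatment, regardless of grade". Section 6.3 brings serious events onto the CRF as well: "This includes events that meet the International Conference on Harmonization (ICH) definitions for a serious adverse event". The word *new* is not defined.

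The safety endpoint in Section 9.2.2 is "Grade 2 or higher AEs, treatment discontinuations". Section 9.6 summarises Grade ≥2 adverse events by arm and compares the arms by Fisher's exact test, visit by visit. Neither section defines a treatment-emergent or worsened event, and neither sets a new reference point when Arm B starts DP at Week 12. Section 9.7 has the study team (monthly, pooled) and the DAIDS clinical representative (quarterly, by arm) look at every sign and symptom of Grade 2 or above.

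Section 6.3.6 treats laboratory tests differently. All required screening and Entry values go on the CRF, and the later rule carries no newness condition: "For post-entry assessments, record on CRFs all Grade ≥ 2 laboratory values".

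**The concern.** A drug-related symptom can appear as an existing mild complaint that gets worse. Table 1 in Section 2.3 shows dizziness and headache more often with DP plus warfarin than with placebo plus warfarin, and both are complaints a subject may already have at Entry. A recording rule that depends on whether the symptom is new, and not on whether its grade has risen, can leave out this form of intolerance.

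An event that is not on the CRF is not in the study database. Source notes may hold it, but nothing in Section 9 draws the endpoint from source notes. Tolerability is Objective 1.3.5 and its threshold is Grade 2, the grade at which the gap lies. If such events occur, the count in each arm is too low and the difference between arms is too small.

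**Working it through.** The documents state no adverse-event rate, safety power or symptom prevalence at Entry, so there is no figure to reproduce. The check is first textual, then illustrative.

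**1. Meaning of *new*.** In the same section, the paragraph on the targeted physical exam names symptoms already identified and new ones as two separate classes. On that usage, a symptom noted at Entry is not new when its grade rises.

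**2. One subject traced through the rules.** Take Grade 1 headache at Entry that is Grade 2 at Week 8, not serious, with drug continued.
- Entry rule: the Grade 1 headache is recorded.
- New-symptom rule: not met.
- Treatment-change rule (read as study treatment): not met. Section 7.1.4 says "Subjects who develop Grade 2 headache may continue study medication", and Section 7.1.1 leaves continuation to the investigator for Grade 1-2 events generally, which covers dizziness.
- Serious-event rule: not met.
- Post-entry diagnosis list in 6.3.5: headache and dizziness are not on it.

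No rule requires the Grade 2 event on the CRF.

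**3. Worsening that is captured.** Related Grade 3 and 4 events hold drug under 7.1.1, and related Grade 3-4 hypotension and headache stop it under 7.1.3 and 7.1.4. These meet the treatment-change rule. Serious events are recorded, and hypotension is on the diagnosis list. What remains is non-serious Grade 2 worsening with no treatment change, plus the smaller group of non-serious events of Grade 3 or above judged unrelated, with drug continued.

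**4. Against Section 9.7.** Review of every Grade ≥2 symptom cannot be guaranteed from records that need hold only the new ones.

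**5. Direction.** Let e1 and e0 be the true Grade ≥2 rates on DP and placebo, and b the share with the symptom at Entry, equal in expectation by randomization. Assume that worsening is unrecorded in that share and no likelier there than in others. The recorded rates are (1−b)e1 and (1−b)e0, and their difference is (1−b)(e1−e0). If e1 = e0, the difference is zero for any b.

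**6. Illustration at 20 per arm (Section 9.4), one visit, two-sided Fisher test at 5%.**
- 5 v 0: p = 2 × C(20,5)/C(40,5) = 2 × 15,504/658,008 = 0.047.
- 4 v 0: p = 2 × C(20,4)/C(40,4) = 2 × 4,845/91,390 = 0.106.

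One unrecorded event can therefore decide the result. Exact power by enumeration, with all rates and all values of b assumed:

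| True rates, DP v placebo | b = 0 | b = 10% | b = 20% | b = 30% |
|---|---|---|---|---|
| 30% v 5% | 45% | 38% | 31% | 24% |
| 40% v 5% | 72% | 64% | 56% | 47% |
| 50% v 10% | 74% | 66% | 58% | 49% |

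For 40% v 5% with b = 20%, the recorded rates are 0.8 × 0.40 = 0.32 and 0.8 × 0.05 = 0.04, a difference of 0.28 in place of 0.35.

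**7. A lower illustration from Table 1.** The excess over placebo is 13.6 − 8.2 = 5.4 points for dizziness and 2.3 − 0.0 = 2.3 for headache, together 7.7 points if no subject has both. Treating every case as Grade ≥2, although the table gives no grades, the excess is 0.077 × 20 = 1.54 subjects. With b from 10% to 40% (assumed), 0.15 to 0.62 of these would be lost. Table 1 comes from heart-valve patients on warfarin, so this is no estimate for the trial.

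**The case against.** The strongest reply is that *new* can mean newly at Grade 2, in which case the worsened headache is recorded. Section 9.7's reference to all such symptoms fits that reading, and Section 11.4.1 sends all adverse events to the IDSMB. This stands as far as showing that the wording is ambiguous. It does not remove the point: the section's own usage favors the narrower meaning, staff could apply the rule differently, and a report to the IDSMB does not put the event on the CRF. The rule also sets a minimum, so staff may record more, but an endpoint should not depend on that.

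Three stronger readings are tempting, and the documents do not support them.
- *All worsening is missed.* Step 3 shows that most severe, serious or treatment-changing worsening is captured. So is laboratory worsening to Grade ≥2.
- *The endpoint counts laboratory abnormalities that predate DP.* Section 4.1.8 admits raised bilirubin ("except if hyperbilirubinemia is secondary to atazanavir"), and Section 6.3.6 would record it again at later visits. But Entry laboratory values are all on the CRF, so such values can be recognized and set aside. Neither 9.2.2 nor 9.6 says that a Grade ≥2 laboratory value is an adverse event, and 9.7 lists the two separately. This is an unstated analysis convention, with no data lost. Adding up repeat records over visits would also overstate it, because the Fisher test is run per visit and after Week 12 both arms are assigned DP.
- *The rule biases the comparison between arms.* It applies equally to both blinded arms, so with no true effect it produces no expected difference.

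It is also fair to say that safety is a secondary objective in a 40-subject pilot, and that a per-visit Fisher test is weak even with complete records.

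**Conclusion.** The point holds in limited form. On the plain reading of Section 6.3.5, non-serious worsening to Grade 2 of a symptom present at Entry, with no treatment change, is not required on the CRF. Those events fall under the trial's own Grade ≥2 endpoint, cannot be recovered from the CRF, and are at odds with the review promised in Section 9.7. The consequence is lower event counts in each arm and less sensitivity to a DP effect.

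The documents do not allow the loss to be sized. It ranges from a fraction of one subject under the Table 1 illustration to a fall in power from 72% to 47% under the 40% v 5% scenario with 30% symptomatic at Entry. Both rest on assumed prevalence at Entry and on worsening being no likelier in subjects who already have the symptom. If it is likelier, the loss is larger. The change is worth making because the loss is permanent and the correction is short.

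**What to change.** In Section 6.3.5, replace the *only new* condition by Grade ≥2 signs and symptoms that are new, recurrent after resolution, or increased in grade. Judge these against the status at Entry and, for Arm B after crossover, against the status at Week 12 before DP starts. The recurrence clause keeps a fresh on-study episode of a symptom that had resolved before Entry. The Week 12 reference keeps symptoms that began on placebo from being counted as arising on DP. Grade 1 symptoms at Week 12 are not on the CRF under the present rule, so symptoms of all grades should be recorded at that visit as they are at Entry. Doing this for every subject avoids any need for the site to know the arm. Sections 9.2.2 and 9.6 should then use the same definition.

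As a secondary clarification, Section 9.6 should state whether Grade ≥2 laboratory values count as adverse events. If they do, they should count only when worse than the value before the treatment period.

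The cost is revised CRF wording, one further all-grade symptom record at an existing visit, a few more entries, and a slightly higher symptom count. No visit, test or clinical management rule changes.
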